9.6.4 Vital Signs

Vital signs data listings will be reviewed for each subject. Summaries of heart rate and blood pressure data over time and change from baseline will be provided.

9.6.5 Physical Measurements

The analyses of physical measurements (weight, BMI and waist circumference) will include summary statistics at each protocol scheduled visit by cohort and by treatment.

9.6.6 Electrocardiogram

All on-study ECG data listings will be reviewed.

Each ECG will include the following measurements: QRS, QT, QTc, RR, and PR intervals. The Fridericia's (QTcF) QT correction and Bazett's (QTcB) QT correction will be computed as specified in section 5. All ECG parameters will be summarized over time and change from baseline over time will be provided.

Further, subjects' maximum change from baseline in QTcF and QTcB will be categorized in following categories and the number and percentage of subjects in each group will be summarized. Unscheduled assessments will be included in the determination of the maximum change.

- ≤ 30 msec
- > 30 60 msec
- > 60 msec

Subjects' maximum post baseline values in QTcF and QTcB will also be categorized in the following categories and the number and percentage of subjects in each group will be summarized.

- ≤ 450 msec
- > 450 480 msec
- > 480 500 msec
- > 500 msec

9.6.7 Antibody Formation

The incidence and percentage of subjects who develop anti-AMG 598 antibodies (binding and if positive, neutralizing) at any time will be tabulated by cohort and by treatment.

Antibody data will be listed for each subject.

9.6.8 Exposure to Investigational Product

The number of doses of IP and the proportion of subjects receiving each dose level will be summarized using descriptive statistics.

9.6.9 Exposure to non investigational product

Descriptive statistics of the number of doses of liraglutide received by each subject will be produced for cohorts 2, 4, 6 and 7.

9.6.10 Exposure to Concomitant Medication

Number and proportion of subjects receiving concomitant medication will be summarized by preferred term for each cohort and treatment as coded by the World Health Organization Drug dictionary.

9.7 Analyses of secondary and exploratory endpoints

9.7.1 Analyses of Pharmacokinetic Endpoints

The Clinical Pharmacology Modeling and Simulation (CPMS) group at Amgen will perform this part of the analysis. The analysis will be performed using the PK analysis set.

Serum AMG 598 concentrations will be determined using a validated assay.

Individual serum concentration-time plots for AMG 598 will be presented for each subject as well as mean concentration-time plots for each dose cohort. PK parameters including

but not limited to AUC, Cmax and tmax will be estimated using either compartmental (eg, PK modeling) or non-compartmental methods.

Actual dosing and sampling times will be used for calculation of PK parameters.

Summary statistics will be generated for each PK parameter for each dose cohort.

Liraglutide PK concentrations will be summarized.

9.7.2 Exploratory Endpoints

9.7.2.1 Pharmacodynamic Parameters:

Absolute values, change values and percent change from baseline values will be summarized in a table for following parameters:

- fasting glucose, insulin, c-peptide, glucose dependent insulinotropic polypeptide (GIP), glucagon-like polypeptide type 1 (GLP-1), glucagon, and free fatty acid (FFA)
- Concentration-time profiles and AUC for metabolic parameters following a MMTT
- Lipid levels, including but not limited to, total cholesterol, low density lipoprotein cholesterol, high density lipoprotein cholesterol, and triglycerides
- Hemoglobin A1c

Graph of mean percent change from baseline by visit for all treatment groups will be provided for all PD parameters.

Additionally, a subset of these parameters (glucose, insulin, C-peptide, GIP, GLP-1, glucagon, and free fatty acids) will be measured on Day -1 and Day 6 postdose (ie. post IP administration) and day 64 postdose after meals during a MMTT and for these parameters, absolute values and percent change from baseline values will be summarized by cohort and treatment.

Graph of grometric mean (+/- SE) vs. time (in minutes) for days -1, 6 and 64 will be plotted for glucose, insulin, C-peptide, GIP, GLP-1, glucagon, and free fatty acids following MMTT.

9.7.2.2 Bone Mineral Density by DXA

Summary of absolute and percent changes in bone mineral density at the lumbar spine, femoral neck and total hip, as measured by DXA, will be summarized for subjects enrolled in cohorts 1-6.

9.7.2.3 Whole Body Composition by DXA

Summary of absolute and percent change from baseline values in body composition, including measures of total bone mineral context (BMC), total fat mass, total lean mass and visceral adipose tissue (VAT), as measured by whole body DXA will be summarized for subjects in cohort 7.

9.7.2.4 Weight, Waist Circumference and BMI:

Summary of absolute and percent change from baseline values in body weight, weight circumference and BMI will be summarized.

Mean percent change from baseline in weight by visit for all treatment groups will also be graphed.

10. Changes From Protocol-specified Analyses

There are no changes to the protocol-specified analyses.

11. Literature Citations / References

Amgen. AMG 598 Investigator's Brochure, Edition 1.

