3.1 Study Rationale

Obesity is a growing global health crisis that is in critical need of safe and effective therapies. Currently approved products provide modest weight loss from baseline with issues of discontinuation due to the side effects of nausea and GI intolerability, as well as lack of continued efficacy. The current study evaluates the safety and tolerability, PK, and PD of multiple ascending doses of AMG 598 alone, and in combination with liraglutide, as a potential weight loss therapy for subjects with obesity. AMG 598, a human monoclonal antibody, binds the glucose dependent insulinotropic polypeptide receptor (GIPR), and blocks the binding of its endogenous ligand (glucose-dependent insulinotropic polypeptide [GIP]) preventing activation of the receptor and downstream pathways. Nonclinical animal studies demonstrated that GIPR antagonism resulted in significant (5-8%) weight loss compared to vehicle control. When combined with commercially available glucagon-like peptide-1 (GLP-1) receptor agonists, AMG 598 lead to a > 20% weight reduction in overweight and obese animals. Thus, in addition to evaluating AMG 598 safety and tolerability, PK and PD alone or in combination with liraglutide (a GLP-1 receptor agonist), the current study also examines the safety and preliminary weight loss efficacy of AMG 598 in a cohort of subjects who have been maintained on a stable dose of liraglutide. The sample size for this specific cohort (30:30 subjects in cohort 7) is based on practical considerations and statistical analysis for the detection of meaningful weight loss. The rationale for dose selection was based on PK and safety analysis of preliminary data collected in the first-in-human (FIH) single ascending dose study of AMG 598 in subjects with obesity. The blinded safety data from the AMG 598 FIH study suggests single doses of AMG 598 have been generally well tolerated up to 560 mg SC, with no serious adverse events (SAE), deaths, or withdrawals related to adverse events reported.

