10.1 Sample Size Determination

The sample size for the study is based on practical considerations. For safety considerations, with up to 66 subjects receiving AMG 598 (6 subjects in each of cohorts 1-6 and 30 subjects in cohort 7), there is a 96.6% chance of detecting an adverse event with a true incidence rate of 5% or greater and a 99.9% chance of detecting an adverse event with a true incidence rate of 10%.

In cohort 7, with a sample size of 30 subjects per group, there is approximately an 80% probability of observing a mean treatment difference in percent change from baseline in body weight between AMG 598 and placebo of > 3%, assuming a true treatment difference of 5%. This assumes a standard deviation for percent change from baseline in body weight of 7% in each treatment group.

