3.2 Sample Size

Approximately 108 subjects (8 per cohort, cohorts 1-6; 60 in cohort 7) will be enrolled.

The sample size for the study is based on practical considerations. For safety considerations, with up to 66 subjects receiving AMG 598 (6 subjects in each of cohorts 1-6 and 30 subjects in cohort 7), there is a 96.6% chance of detecting an adverse event with a true incidence rate of 5% or greater and a 99.9% chance of detecting an adverse event with a true incidence rate of 10%.

In cohort 7, with a sample size of 30 subjects per group, there is approximately an 80% probability of observing a mean treatment difference in percent change from baseline in body weight between AMG 598 and placebo of > 3%, assuming a true treatment difference of 5%. This assumes a standard deviation for percent change from baseline in body weight of 7% in each treatment group.

Replacement of subjects:

Subjects who withdraw from the study or who discontinue study drug administration prematurely may be replaced at the discretion of Amgen in consultation with the investigator. The replacement subject will be assigned to receive the identical treatment as the replaced subject.

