9.1 General Considerations

Descriptive statistics will be provided for selected demographics, safety, PK and PD endpoints. Descriptive statistics on continuous measurements will include means, medians, standard deviations and ranges, while categorical data will be summarized using frequency counts and percentages. Data will be presented and summarized by treatment at each time point, as applicable. Graphical summaries of the data may also be presented.

Data for subjects receiving placebo will be combined across cohorts 1, 3 and 5 (monotherapy cohorts) and separately across cohorts 2, 4 and 6 (combination therapy cohorts). Placebo data for subjects in cohort 7 will not be combined with other cohorts.

Data for subjects receiving AMG 598 will be presented separately by cohort.

When data are summarized by time, the values recorded against the scheduled time points listed in the protocol will be used. When assessing minimum/maximum increases or decreases over the study, all assessments, including unscheduled assessments will be used.

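### Cohort 7 is sized partly on a between-arm weight difference that the SAP does not plan to estimate, and the SAP's baseline and analysis sets can be read as starting at the day -28 run-in placebo

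*SAP*

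**What the plan says.** **Sizing.** Protocol 10.1 opens by saying "The sample size for the study is based on practical considerations". For cohort 7, Protocol 3.1 goes further: the size "is based on practical considerations and statistical analysis for the detection of meaningful weight loss". Protocol 10.1 and SAP 3.2 put this in numbers. With 30 per group there is "approximately an 80% probability of observing a mean treatment difference in percent change from baseline in body weight" above 3%, if the true difference is 5%. The variability input is given as follows: "This assumes a standard deviation for percent change from baseline in body weight of 7% in each treatment group". Neither sizing statement names a visit.

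**Analysis of weight.** SAP 9.7.2.4 says "Summary of absolute and percent change from baseline values in body weight, weight circumference and BMI will be summarized" and "Mean percent change from baseline in weight by visit for all treatment groups will also be graphed". SAP 9.6.5 adds that physical measurements "will include summary statistics at each protocol scheduled visit by cohort and by treatment". SAP 9.1 says "Data will be presented and summarized by treatment at each time point, as applicable" and lists means, medians, standard deviations and ranges. Efficacy analyses are marked not applicable in both documents. SAP 4.1 allows baseline as a covariate but names no model. Protocol 10.3.2.4.2 gives no method for exploratory endpoints and assigns them to the safety analysis set.

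**Anchor date in cohort 7.** Every cohort 7 subject receives a placebo injection on day -28 as part of a run-in (Protocol 5.1 and Table 2-3) and is randomized on day 1 (Protocol 7.2). SAP 5 and SAP 6 define baseline, Study Day 1 and the analysis sets by the first dose, or any one dose, of investigational product, which SAP 5 defines as AMG 598 or placebo.

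**The concern.** The quantity used to justify 60 subjects is a contrast between two arms. The planned output describes each arm separately. A reader who wants to compare the result with the planning assumption must choose a visit, subtract two means and work out an interval by hand. Nothing reported shows directly how precise the cohort's preliminary weight-loss result is.

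The second part concerns what change from baseline means in this cohort. If the run-in placebo counts as the first dose, baseline is the screening or day -28 weight. Weight change during the run-in then enters every percent-change summary. The analysis sets would also include people who left before randomization. Randomization means this would not favour one arm on average, but each arm's change would no longer be change since the start of randomized treatment.

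**Working it through.** **1. The plan's own figure.** Inputs from Protocol 10.1 and SAP 3.2: 30 per arm, SD 7% in each arm, true difference 5 points, threshold 3 points.

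- SE of the difference = 7 × √(1/30 + 1/30) = 1.807 points.
- P(observed > 3 | true 5) = Φ((5 − 3)/1.807) = Φ(1.107) = 86.6%. The documents state approximately 80%, so the literal wording does not reproduce it.
- Normal-approximation power of a two-sided 5% test to detect 5 points = Φ(5/1.807 − 1.96) = 79.0%. This is close to 80% but is a different quantity, and the documents name no test.

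The sponsor should say which quantity is meant. The point below does not depend on the answer.

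**2. Precision of the sizing contrast.** A 95% level is assumed, because the documents give none.

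- Half-width = t(0.975, 58) × SE = 2.0017 × 1.807 = 3.62 points.
- Observed 3 points: 3 ± 3.62 = −0.62 to 6.62.
- Observed 5 points: 5 ± 3.62 = 1.38 to 8.62.
- With fewer weights at the chosen visit (assumed): 27 per arm gives 3.82 points and 24 per arm gives 4.07.
- Adjusting for day 1 weight narrows the interval only as far as that weight predicts percent change. At an assumed correlation of 0.3, the half-width is 3.62 × √(1 − 0.3²) = 3.45.

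The 3-point planning threshold is smaller than the half-width, so an observed difference just above 3 points would not exclude zero.

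**3. Visits.** Table 2-3 schedules cohort 7 weight after day 1 on days 15, 29, 57, 71, 85, 145 and 207, which is seven visits. Neither document says which visit the 7% SD or the 3% and 5% differences refer to.

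**4. Anchor date, side by side.**

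| Item | SAP | Protocol |
|---|---|---|
| Baseline | Last assessment before the first dose of investigational product, defined as AMG 598 or placebo (SAP 5) | Section 9.2.3.4 sets day 1 pre-dose, for ECGs only |
| Day 1 | First day investigational product is given (SAP 5) | Cohort 7: first dose after randomization (9.1.2) |
| Safety set | At least one dose (SAP 6.1) | At least one dose on day 1 (10.2.1.1) |
| Final analysis set | Cohort 7 subjects with at least one dose (SAP 6.5) | Not defined |
| Cohort 7 randomization | Scheduled for day -28 (SAP 5, Enrollment Date) | Day 1 (7.2) |

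Read literally, the day -28 placebo satisfies every SAP definition in the middle column. Protocol 6 and 6.6 say that subjects who fail the run-in are removed before randomization. They would still have had one dose, so they meet SAP 6.1 and 6.5. SAP 10 nevertheless declares no changes from the protocol-specified analyses.

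**The case against.** **Descriptive reporting is a declared choice.** Weight is exploratory in a phase 1b study with a safety objective. The sizing sentence speaks of observing a difference and names no test or significance level. Means and SDs by arm will be shown at every scheduled visit, so a reader with the visit counts can derive an unadjusted difference and interval. All of this stands. It makes the gap one of presentation and pre-specification, not of validity.

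**A multiplicity problem?** A reader might infer that leaving the visit open inflates a false-positive rate against the 3% criterion. The documents do not support that. Three percent appears only in the sizing statements; no success, go/no-go or dosing decision is tied to it, and no visit can be hidden. With no true effect, the chance of an observed difference above 3 points is 1 − Φ(3/1.807) = 4.8% at one visit. For at least one of seven visits it ranges from about 5% to 24%. That depends on the assumed between-visit correlation (0.5 to 0.9, equal or first-order autoregressive) and on whether the SD is 7% throughout or grows with the square root of time. The documents give neither input, so no weight should rest on this figure.

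**Is the anchor date really open?** Protocol 9.1.2 and 10.2.1.1 point clearly to day 1, and day numbering itself implies that day -28 comes before Day 1. Subjects who fail the run-in have no randomized arm, so they should not reach a by-treatment weight table. Day 1 is therefore very probably the intention. But the SAP's definition of Study Day 1 does not settle it, because the first day investigational product is given is, under the SAP's own definition of that product, the run-in day. The SAP also omits the protocol's day 1 qualifier and gives a different randomization day.

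**Conclusion.** The point holds at the level of something to consider. The SAP does not specify an estimate, an interval or a reference visit for the contrast that partly justifies cohort 7's size. At the planning assumptions (SD 7%, 30 per arm, 95% level) that contrast is known to within about ±3.6 points, and the reader would not be told so directly. A stated interval would show this precision without materially changing it.

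The baseline and analysis-set wording is a genuine conflict between SAP and protocol and needs correcting even if reporting stays purely descriptive. Its numerical effect cannot be sized, because the documents give no run-in weight change or run-in failure rate.

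The documents do not support reading this as an invalid analysis, as selective reporting of visits, or as an uncontrolled error rate.

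**What to change.** 1. **SAP 5, 6.1 and 6.5.** State that for cohort 7 the first dose of investigational product, Study Day 1, baseline and the analysis sets refer to the first dose after randomization, on day 1, and not to the day -28 run-in placebo. Correct the cohort 7 randomization day to match Protocol 7.2.
2. **SAP 9.7.2.4.** Add, for cohort 7 and labelled exploratory: *The AMG 598 minus placebo difference in percent change in body weight from the day 1 pre-dose value will be estimated with a two-sided 95% CI by ANCOVA (treatment, day 1 weight) at one visit, day 85 or another single visit named before cohort 7 data are unblinded, in randomized subjects dosed on day 1.*

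A repeated-measures model is optional. With seven visits, an unstructured covariance has 7 × 8/2 = 28 parameters for about 60 subjects, which is more than this gap requires. Keep the descriptive tables and the graph.

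The cost is a few lines of SAP text and one extra exploratory table in an otherwise descriptive report, with no new data or visits.

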Appendix A. Handling of Missing or Incomplete Dates for Adverse Events and Concomitant Medications

14.1.1 Imputation Rules for Partial or Missing Stop Dates:

If the month and year are present, impute to the last day of the month.

If only the year is present, impute December 31 of that year.

If the stop date is entirely missing, assume the event or medication is ongoing. If a partial or complete stop date is present and the 'ongoing' or 'continuing' box is checked, then it will be assumed that the AE or conmed stopped and the stop date will be imputed, if partial.

	Stop Date							
		Complete: yyyymmdd		Partial: yyyymm		Partial: yyyy		
Start Date		<1 st Dose	≥1 st Dose	<1 st Dose yyyymm	≥1 st Dose yyyymm	<1 st Dose yyyy	≥1 st Dose уууу	Missing
Partial: yyyymm	Equal to 1 st Dose yyyymm		1		1	N/A	1	1
	Not equal to 1 st Dose yyyymm	2	2	2	2	2	2	2
Partial:	Equal to 1 st Dose yyyymm		1		1	N/A	1	1
уууу Уууу	Not equal to 1 st Dose yyyymm	3	3	3	3	3	3	3
Mis	sing	4	1	4	1	4	1	1

14.1.2 Imputation Rules for Partial or Missing Start Dates:

1 = Impute the date of first dose

2 = Impute the first of the month

3 = Impute January 1 of the year

4 = Impute January 1 of the stop year

Note: For subjects who were never treated (first dose date is missing), partial start dates will be set to the first day of the partial month.

Note: If the start date imputation leads to a start date that is after the stop date, then do not impute the start date.

Appendix B. Reference Values/Clinical Severity grading

The clinical severity grading scale is as follows:

- grade 1 = mild (e.g., asymptomatic or mild symptoms, clinical or diagnostic observations only, intervention not indicated, or does not interfere with activity)
- grade 2 = moderate (e.g., minimal intervention indicated or interferes with activity)
- grade 3 = severe (e.g., medically significant but not immediately lifethreatening, prevents daily activity, or requires treatment)
- grade 4 = life-threatening (i.e., refers to an event in which the subject was, in the view of the investigator, at risk of death at the time of the event)
- grade 5 = fatal
